3.3.d.i. Psychiatric diagnoses: The SCID for DSM-4 Clinician Version (SCID-CV) is a fairly brief version of the SCID that assesses Axis I disorders in DSM-4 including MDD, dysthymic disorder, bipolar disorders, schizophrenia, anxiety disorders, eating disorders, and drug/alcohol abuse/dependence. **3.3.d.ii. Depression and anxiety measures:** A 2-item self-report screening tool for depression (2-SRSD) taken from the Primary Care Evaluation of Mental Disorders Procedure (PRIME-MD) screening interview will be used to detect suspected cases of depression among asthma clinic caregivers.⁵⁵ This instrument had better sensitivity (96%) than either the Center for Epidemiologic Studies Depression Scale (CES-D) (93%) or BDI (89%) in identifying depression as defined by structured clinical interview in a general medical clinic.⁵⁵ Specificity of the 2-SRSD was 57%. A positive answer to either 1) “During the past month, have you often been bothered by feeling down, depressed, or hopeless?” or 2) “During the past month, have you often been bothered by little interest or pleasure in doing things?” will be considered a possible case of depression and qualify for further assessment. [name] has used this screening tool in prior studies including an ongoing NHLBI-funded study in adults with asthma. The HRSD (17-item version)⁴⁷ is an observer-rated measure of depressive symptomatology. The HRSD will be given at every visit. Because of its wide use for many decades, the HRSD will be the primary measure of caregiver depressive symptoms in the study. The QIDS-SR⁴⁸ is a validated 16-item self-report scale that assesses depressive symptom severity. Scores of ≤ 7 are considered normal, 8-12 suggest mild depressive symptoms, 13-16 moderate depressive symptoms, 17-20 moderate to severe depressive symptoms, and ≥ 21 severe depression. The use of these two depression instruments allows us to assess changes in both clinician-rated and self-reported depressive symptoms and their relationship to asthma outcomes. Perceived Stress Scale (PSS) is a 10 question self-report measure validated in middle school children and adults, and available in both English and Spanish. This instrument will be administered to the caregiver and the child at each visit, and will allow for detection of changes in stress levels that are not as severe as depression and anxiety. Research coordinators will assist younger children, if necessary, by helping them read and understand the questions. The Relatedness Questionnaire is a validated 17-item questionnaire completed by the child regarding his or her primary caregiver. It will assess the quality of the child’s self-reported relationship with the caregiver.⁵⁷ Screen for Child Anxiety Related Disorders (SCARED) is a 41-item self-report scale, validated in

both English and Spanish. This scale has 3-point response options and assesses children's anxiety level within the last 3 months.⁵⁸ The Children's Depression Inventory Full Length (CDI Full Length) is a 27-item self-report scale designed to assess depression in children and validated in both English and Spanish.

The COVID-19 Interview is intended to take into account the impact of the COVID19 pandemic on the factors under study in our research. One goal is to assess whether caregiver depression and child asthma control worsened after the onset of the COVID19 pandemic. We will accomplish this by comparing the severity of caregiver depression and the degree of control of the child's asthma in the months before the COVID19 to the caregiver severity depression of and control of child's asthma during the COVID19. This is data that is collected under the currently approved study protocol. In addition, one of our IRB approved research staff and/or a study psychiatrist will ask the caregivers to report on the perceived impact of COVID19 on their own emotional state and functioning, and on the emotional state and asthma control in their child.

3.3.d.iii. Quality of Life: The Pediatric Asthma Caregiver's Quality of Life Questionnaire (PACQOL)⁵⁹ measures the problems that the parents of children with asthma experience as a result of their child's asthma. There are 13 questions in 2 domains (activity limitations and emotional function) that were selected on the basis of their importance to the parents themselves. The questionnaire is self-administered and has 7-point response options. Pediatric Asthma Quality of Life Questionnaire (PAQOL)⁵⁹ measures problems that children experience as a result of their asthma. It has 23 items in 3 domains (symptoms, activity limitations, emotional function); 3 of the activity questions are "patient-specific" and identified by the patient at the beginning of the study. Items were selected on the basis of their importance to the children themselves. The questionnaire has 7-point response options and takes approximately 10 minutes to complete. California Verbal Learning Test (CVLT-II or CVLT-C for children under 16 years of age) is a validated assessment that measures episodic verbal learning and memory, and is sensitive to the effects of inhaled corticosteroids that many child participants with asthma take daily. CVLT consists of 16 nouns read aloud to the participant in one-second intervals over five learning trials. After each trial, participants are asked to recall as many words as they can in any order.

3.3.d.iv. Asthma Severity, Control and Outcomes: Asthma outcome measures to be used in this study will adhere to the recommended asthma clinical research core outcome measures recently proposed by the NIH's Asthma Outcomes Workshop.⁶⁰ We will incorporate information on asthma exacerbations, healthcare utilization, pulmonary function, quality of life, composite control scores, and asthma symptoms into our outcome measures. Exacerbations will be assessed by caregiver report at each study visit. Exacerbation outcomes will include systemic steroid courses, asthma-specific hospitalizations, asthma-specific emergency department visits/urgent care visits, and asthma-specific intensive care unit admissions/intubations since the last appointment. Healthcare utilization relating to each child's asthma will be assessed, including asthma-specific hospitalizations, asthma-specific emergency department visits/urgent care visits, asthma-specific outpatient visits, and asthma-specific medication use. The number of asthma-specific hospitalizations, emergency department visits and unscheduled clinic appointments by the child in the prior year and during the 1 year of the intervention will be assessed by caregiver report using a calendar to facilitate recall. This information will be supplemented with data obtained directly from the child's hospital, primary physician/asthma specialist, and pharmacy records.

Spirometry data, including % predicted of FEV₁, forced vital capacity (FVC), and FEV₁/FVC ratio will be collected on the child at all study visits using a portable spirometer (EasyOne Plus, NDD Medical Technologies, Inc. Andover, MA).

As a measurement of asthma control, the Asthma Control Test (ACT) will be administered to children ages 12+ at each caregiver depression study visit and the Childhood Asthma Control Test (cACT) will be administered to children ages 5-11.^{61, 62} The ACT and cACT tools represent a continuum of asthma control assessment tools across childhood age ranges. In both tools, a score of > 19 signifies controlled disease and scores of ≤ 19 signifies uncontrolled asthma. Thus, the scores can be combined in the data analysis.

The Composite Asthma Severity Index (CASI) will be obtained on the child at baseline and at all study visits.⁶³ CASI was developed by the National Institutes of Health-supported Inner City Asthma Consortium (ICAC) and includes five domains: day symptoms and albuterol use, night symptoms and albuterol use, controller treatment, lung function measures, and exacerbations. The CASI tool has been validated to assess asthma severity in children between 6 and 20 years of age. Because it combines domains of impairment and treatment level to assess asthma severity, the CASI score remains steady through changes in standard guidelines-based asthma care (i.e. step-up or step-down asthma controller therapy). Therefore, it has utility in assessing response to new asthma treatment/intervention modalities such as our proposed intervention, which may not only alter asthma symptoms but the requirement for asthma controller treatments as well.⁶³

3.3.d.v. Adherence: CAMPCS medication adherence interview is a brief 9-item clinician-rated scale assessing controller medication adherence in the past week that can be administered over the phone or in person.⁶⁴ The CAMPCS interview, along with its specific manner of presentation, has established reliability and validity.⁶⁵ The interview shows impressive sensitivity to asthma inhaler adherence, assessed via electronic monitoring.⁶⁶

3.3.d.vi. Medication Side Effects and Adverse Events: Antidepressant side effects and adverse events will be inquired about at each clinic and phone visit. In addition, The Psychobiology of Recovery in Depression III - Somatic Symptom Scale (PRD-III),⁶⁷ a 24-item side effects rating scale developed for a longitudinal depression study at the University of Pittsburgh, will be utilized to formally assess somatic complaints. The PRD-III covers a wide range of common medication side effects and can be quickly and easily administered by a clinician. [name] has used this scale in numerous prior studies. Spirometry results at each visit will be also used to evaluate whether the children need to follow up with their primary care provider or the emergency room. [name] has designed a safety protocol to ensure that if any of the following signs/symptoms are present, then a child needs to be referred to the medical doctor or the emergency services: albuterol use prior to the study visit more closely spaced than every 4 hours, child's FEV₁ on spirometry is 50% predicted or less, caregiver is concerned that child's is experiencing a significant asthma attack. Additionally, the children will be immediately referred to 911/emergency room for transport in presence of the following: child can't talk without gasping/losing breath, child is hunched forward with deep breathing, chest/neck pull is during each breath, nostrils flaring (open wide) during each breath, lips or fingertips look blue.

3.3.e. Assessment Training

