Results: Mean age of the caregivers was 34.2 ± 7.3 years, and 96% were women. Both depressive (26%) and anxiety disorders (22%) were common. Caregivers with clinically significant elevations in the anxiety or depression BSI subscales reported more asthma-related hospitalizations for the child in the past 12 months than did caregivers with lower BSI scores (all $p < 0.05$). Asthma-related hospitalizations correlated with BSI total ($r = 0.20$, $p \leq 0.01$), anxiety ($r = 0.21$, $p < 0.01$), and depression ($r = 0.16$, $p \leq 0.05$) subscale scores. Caregiver psychiatric diagnosis of an anxiety disorder (n = 36) was associated with 43% more asthma-related hospitalizations (2.0 ± 2.5 vs. 1.4 ± 1.2 , $p < 0.05$) in the child while current caregiver depression (n = 44) was associated with 50% more unscheduled clinic visits (3.0 ± 3.4 vs. 2.0 ± 2.6 , $p < 0.05$).

Significance: This study demonstrates that the Diagnostic and Statistical Manual of Mental Disorders (DSM-IV)-defined psychiatric disorders, particularly depressive disorders, are common in asthma caregivers and associated with a greater frequency of asthma-related service utilization by the child. The study also supports feasibility by demonstrating that we can enroll large numbers of caregivers in a research study.

3.3.a.ii. Pilot Study 2: Antidepressant Treatment of Caregivers of Children with Asthma Improved the Child's Asthma: This pilot study, conducted in Dallas, examined the impact of antidepressant treatment on the caregiver's depression and the child's asthma.³⁵

Methods: Eight currently depressed asthma caregivers (6 women and 2 men, mean age of 35.8 ± 6.6 years) were enrolled in this intervention study with monthly assessments for 6 months, and received algorithm-based

antidepressant treatment. The children were 5 boys and 3 girls with a mean age of 9.8 ± 3.8 years. Caregiver depressive symptoms were assessed with the Hamilton Rating Scale for Depression (HRSD)⁴⁷ and Quick Inventory of Depressive Symptomatology-Self-Report (QIDS-SR).⁴⁸ Spirometry was obtained and asthma symptoms quantified using the Pediatric Asthma Symptom Scale (PASS). Hospitalizations, emergency room visits, and unscheduled clinic visits were also assessed.

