3.3.b. Overview and rationale of study design: We propose a one-year, repeated measures, within-subject design to examine the impact of improved caregiver depression on child asthma outcomes. A CLPM for longitudinal data will be fit using a maximum likelihood structural equation model (SEM) in order to explore longitudinal mediation between asthma outcomes (asthma control, spirometry, QOL) and depressive symptoms. CLPM will test whether caregiver improvement preceded child asthma improvement, and SEM will test whether improved adherence and/or decreased child anxiety/depression mediated the effect. We considered a randomized control trial, but it would not be ethically acceptable to withhold medication from caregivers diagnosed with MDD for the proposed one-year duration of the study. It is unlikely that potential

participants in the study would find this acceptable. Furthermore a controlled design is not necessary since we are not testing the efficacy of antidepressants for depression, but rather the impact of improvement on caregiver depression on the child.

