3.4. Statistical Analyses

Aim 1. Determine if improvement in depressive symptoms in caregivers of children with asthma predicts subsequent improvement in the child's asthma control. A CLPM for longitudinal data will be fit using a maximum likelihood SEM in order to explore reciprocal causation between asthma outcomes and depressive symptoms with lagged effect. A separate model will be constructed for each asthma outcome (e.g. CASI, ACT, steroid bursts). The full CLPM with all cross-lagged paths will test if both the asthma outcomes and depressive symptoms predict each other at subsequent visits. For each full model, paths will connect the value of the depressive symptom score (e.g. HRSD) at each visit to the asthma outcome (e.g. CASI) at each subsequent visit (e.g. 4 weeks later, 8 weeks later). Another set of paths will connect the asthma outcome at each visit to the HRSD at each subsequent visit. The full model will be compared to reduced models containing either the first set of paths or the second set. We hypothesize that the model with the first set of paths will provide a better fit than the second set. The models will be compared on goodness of fit criteria, a non-significant X^2 p-value .05 or more, fit indices .90 or more, RMSEA .05 or less, and significant path coefficients.⁶⁸⁻⁷⁵ Extensive overviews of the use of this CLPM for longitudinal data analyses are given by Cole and Maxwell and MacKinnon.^{70, 75} We will follow Cole and Maxwell's⁷⁰ guidelines for testing the proposed causal relationship, caregivers' depressive symptoms preceding child's asthma outcomes, with longitudinal data using SEM software *Mplus*. We will control for variables that might impact depressive symptoms or asthma response including age, gender and race/ethnicity. The primary analysis for this aim will use CASI scores for the child and caregiver HRSD scores. The HRSD is a widely used clinician-rated depression scale while the CASI scores take into account both asthma symptoms and asthma medication use to treat symptoms. Similar analysis will be conducted using the QIDS-SR as the depression measure and STAI as a caregiver anxiety measure. ACT scores and steroid bursts will be used as well as CASI scores in the analysis.

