Aim 2. Determine if improvement in depressive symptoms in caregivers of children with asthma predicts reduced unscheduled asthma-related service utilization. Separate analyses will be done for each event (ER visits, hospitalizations and unscheduled appointments). The dependent variable will be a count of the number of times the event occurred during the 52 week study period. This number will be converted to events per month to adjust for subjects who do not complete 52 weeks. The independent variables will be caregiver depressive symptoms as measured by HRSD along with site, baseline depressive symptoms, baseline asthma symptoms, and season of the year. Other baseline demographic and clinical variables (such as child's age) will be added if they improve the fit of the final model. Because the dependent variable is accumulated over the study period, caregiver HRSD will also be summarized over the study period for each subject by computing a seasonally adjusted slope of change over time during the 52 week study. All participants with two or more post-baseline HRSD measurements will be included in the analyses. Count data typically follow a Poisson distribution. Therefore, a generalized linear mixed model with Poisson link function will be used (SAS Proc GLIMMIX). Intercepts will be random effects. If an excessive number of subjects have zero events and the Poisson distribution is not appropriate (which often occurs with count data), then we will consider negative binomial models, zero-inflated Poisson models, and hurdle models. At times caregiver depression may get worse, despite treatment. Therefore, we will examine whether increases in caregiver depressive symptom severity predicts worse child asthma outcomes. The same model used above will be used here except that an indicator variable will be added to indicate if caregiver HRSD scores worsened or stayed the same during the study (zero or positive slope) versus improved (negative slope). The addition of this indicator variable will allow the relationship between change in HRSD and utilization events to differ for those who worsen or stay the same versus those who improve. This aim will be tested by the significance of this additional indicator variable. The primary analysis for this aim will use HRSD scores and ER visits (sensitive to the intervention in Pilot Study #2 and an important clinical outcome). However, similar analysis will be conducted using the QIDS-SR and STAI in place of the HRSD, and using unscheduled clinic visits and hospitalizations.

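### The Aim 1 cross-lagged model does not separate stable family differences from within-family change, so correlated stable levels may produce non-zero lagged paths in either direction

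*Combined protocol and SAP*

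**What the plan says.** Section 3.3.b describes the design: "We propose a one-year, repeated measures, within-subject design to examine the impact of improved caregiver depression on child asthma outcomes". It adds that the CLPM will test whether caregiver improvement came before the child's. The hypotheses in section 3.3.a.viii concern improvement followed by improvement. Section 3.3.c defends open choice of treatment because the aims relate to symptom change, however it is achieved. The question is therefore about change within a family.

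Section 3.4, Aim 1, gives the model: "A CLPM for longitudinal data will be fit using a maximum likelihood SEM in order to explore reciprocal causation between asthma outcomes" and depressive symptoms. In it, "paths will connect the value of the depressive symptom score (e.g. HRSD) at each visit to the asthma outcome" at every later visit, with a mirror set of paths from asthma to depression. On the primary variables: "The primary analysis for this aim will use CASI scores for the child and caregiver HRSD scores". The decision rests on fit criteria, significant paths and a comparison of the two path sets: "We hypothesize that the model with the first set of paths will provide a better fit than the second set". On adjustment: "We will control for variables that might impact depressive symptoms or asthma response including age, gender and race/ethnicity".

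No random intercept, trait factor or centring on the family mean is named. Aim 3 takes over the Aim 1 approach, and Aim 4 fits its models as described for Aim 1. The only random intercepts are in the Aim 2 count model: "Intercepts will be random effects".

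**The concern.** An observed HRSD or CASI score has two parts: a level that stays with the family all year, and a deviation from that level at a given visit. The hypothesis concerns the deviations, but a CLPM on observed scores uses both parts. If families with persistently higher HRSD also have persistently higher CASI, an earlier HRSD score carries information about the child's stable CASI level that the earlier CASI score captures only imperfectly. The lagged path is then non-zero even if no caregiver's improvement is ever followed by a child's improvement.

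This matters because there is no randomised comparison. Sections 3.3.b and 3.5 reject one, partly on the strengths of the within-subject design. Removing stable differences between families is the main protection such a design offers. Age, gender and race/ethnicity cannot remove differences that are unmeasured. Section 3.1 links low income and inner-city residence to asthma morbidity, yet neither is among the covariates named for Aim 1.

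**Working it through.** **Inputs from the documents.** N = 175 and 13 occasions, giving 13 × 12 / 2 = 78 paths per direction (section 3.4, Power). Table 2 lists baseline plus 13 assessments, which is 14 occasions; 13 is used here to match the Power paragraph. Alpha is not stated, and 0.05 is assumed.

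**Inputs assumed.** The documents give no stable share of variance (s), stable-level correlation (r) or within-family autocorrelation (a). I take s = 30-50%, r = 0-0.5 and a = 0.4.

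**The plan's own figures.** Joint F test, λ = f²N, degrees of freedom u and N − u − 1:
- 10 predictors: λ = 0.10 × 175 = 17.5 on 10 and 164 df; power 0.810.
- 78 paths: λ = 0.31 × 175 = 54.25 on 78 and 96 df; power 0.802.

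Both reproduce. They concern precision and do not address this bias.

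**Size of the bias.** Let each standardised score be a stable part (share s in both series) plus an independent AR(1) deviation, with true cross-effect zero. Then corr(HRSD at t−1, CASI at t) = sr, and the lag-1 autocorrelation of CASI is s + (1 − s)a. The coefficient of CASI on earlier HRSD, given earlier CASI, is

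b = s r (1 − s)(1 − a) / (1 − s²r²).

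With s = 0.5 and a = 0.4:
- r = 0: b = 0
- r = 0.2: b = 0.030 / 0.990 = 0.030
- r = 0.3: b = 0.045 / 0.9775 = 0.046
- r = 0.5: b = 0.075 / 0.9375 = 0.080

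With equal shares the formula is the same in the reverse direction.

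**False-positive rate for caregiver-to-child.** True cross-effect zero, N = 175, 13 occasions, s = 0.5, a = 0.4, 200 simulated trials per row. The pooled path and the random-intercept model were tested by likelihood ratio:

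| r | Pooled lag-1 path | 78 paths, lag-1 autoregression | 78 paths, all-lag autoregression | Random-intercept CLPM, pooled lag-1 path |
|---|---|---|---|---|
| 0 | 5.5% | 6% | 6% | 4% |
| 0.2 | 50.5% | 13.5% | 9% | 4% |
| 0.3 | 86.5% | 26.5% | 11% | 4% |
| 0.5 | 100% | 81% | 24.5% | 4% |

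A second simulation over s = 30-50% and r = 0.2-0.3 gave 31-76% for the pooled path, 9-25% for the 78 paths with lag-1 autoregression and 5-8% with all-lag autoregression. A further one of the pooled path, on 14 visits with family-clustered standard errors, gave 29-77%. The likelihood-ratio test of the pooled path runs somewhat higher at the top corner (86.5%). The Monte Carlo standard error with 200 trials is √(0.265 × 0.735 / 200) = 3.1 points at 26.5% and 1.5 points at 5%, so the low end of the all-lag column cannot be told from the nominal rate.

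**Direction.** At s = 0.5, r = 0.3 the mean false path was 0.047 forward and 0.044 in reverse, and the caregiver-to-child set fitted better in 49% of trials. With unequal shares (caregiver 50%, child 30%) it was 0.051 against 0.033, and 55% of trials.

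**Random intercepts.** The 4% is 8 of 200 in each row. A separate check at s = 0.5 gave 8% (5 of 60) at both r = 0.2 and r = 0.3.

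**The case against.** A reader might infer that stable differences will appear specifically as a false caregiver-to-child effect, and that the primary analysis would then confirm the hypothesis. The documents do not support that.

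- **Direction and decision rule.** The bias runs both ways, and Aim 1 turns on which path set fits better. In a simulation of the all-lag model with lag-1 autoregression (s = 30% and 50%, r = 0.2 and 0.3, 150 trials per cell), the caregiver-to-child set fitted better in 46-55% of trials. Neither the full nor the reduced models met the plan's chi-square and RMSEA criteria in any trial; median RMSEA was 0.09-0.13 and 0.07-0.10. Misfit would therefore be visible. This stands in part. The plan may use the criteria to compare models rather than as strict gates, and it does not state the autoregressive order. With all-lag autoregression the criteria give no protection, although the inflation is then smaller. The requirement of significant paths remains exposed.
- **Size.** The 30-76% belongs to a single pooled lag-1 path. The plan's 78-path structure absorbs part of the stable variance. This stands.
- **Evidence for correlated stable levels.** Section 3.3.a.i reports "Asthma-related hospitalizations correlated with BSI total" (r = 0.20), and 0.16 for the depression subscale. If s = 0.5 in both series and all of it were stable, 0.16 would imply r = 0.16 / 0.5 = 0.32. But this is one cross-sectional correlation on another scale and outcome, among caregivers with and without MDD. It makes a non-zero r plausible and does not establish one here.
- **Loss of information.** Section 3.5 relies on a range of depression responses. Random intercepts may partly absorb sustained differences between responders and non-responders. This stands, and it is why making the random-intercept model the sole primary analysis is debatable.

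**Conclusion.** The mismatch is real. The question is within-family, while the Aim 1, 3 and 4 models mix between-family with within-family association, and the three named covariates cannot undo that. The consequence is conditional: the paths are biased only if stable HRSD and CASI levels are correlated, and then in either direction. Under the assumed values (autocorrelation 0.4, stable share 30-50%, stable-level correlation 0.2-0.3), the false-positive rate is about 30-76% for a pooled lag-1 path. For the joint test of the plan's 78 paths it is about 9-25% or 5-11%, depending on an autoregressive order that the plan leaves open. None of these assumptions can be checked against the documents. The conclusion is therefore that a significant caregiver-to-child path from the plain CLPM could not, on its own, be read as a within-family effect. It does not follow that the planned analysis is bound to give a false confirmation.

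**What to change.** In section 3.4:

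1. State that the Aim 1 hypothesis concerns within-family change.
2. Prespecify a random-intercept CLPM for Aims 1, 3 and 4: one random intercept per series per family, the two allowed to correlate, with autoregressive and cross-lagged paths among the within-family deviations. At minimum, make it a sensitivity analysis reported beside the plain CLPM.
3. State the lag order of the autoregressive and cross-lagged paths in both models. The random-intercept check above used lag-1 paths held equal over visits.
4. Claim a within-family effect only if the random-intercept model supports it.

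The cost is SAP wording, three more parameters per model (two variances and a covariance) and some loss of power, which the documents give no basis to quantify. No measurements beyond the visits scheduled in Table 2 are needed.
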